Section 6.3.3 Blinding	Revised text to indicate that all Sponsor personnel except for a blinded medical monitoring team will be unblinded after the last expected Follow-up Week 4 visit, to enable earlier program strategic decision-making by the Sponsor.	
The protocol currently permits select Sponsor personnel to be unblinded during the study. This amendment is being made due to a change in strategy. All Sponsor personnel except for a blinded medical monitoring team will be unblinded after the last expected Follow-up Week 4 visit, to enable earlier program strategic decision making by the Sponsor.
 
All participants and study-site personnel directly associated with study conduct will continue to remain blinded to study intervention assignment through Follow-up Week 8.

Section Number and Name	Description of Change	Brief Rationale
Additional Changes		
Section 1.2 Schema	Added text to footnote “b” to indicate the changes in blinding strategy for the Sponsor.	See rationale for Section 6.3.3
Section 1.3.1 Schedule of Activities (Main)	Added footnote “f” to indicate the changes in blinding strategy for the Sponsor.	See rationale for Section 6.3.3
Section 4.1 Overall Design	Updated to align with the changes in blinding strategy for the Sponsor.	See rationale for Section 6.3.3
Section 9.1 Responsibility for Analyses/In-house Blinding	Changed the word “unblinded” to “locked” in the third sentence of the second paragraph.	For alignment of timing with the changes in blinding strategy for the Sponsor.
Section 9.1 Responsibility for Analyses/In-house Blinding	Revised text to indicate that in addition to the unblinded Sponsor team that has been unblinded since the trial started, all other Sponsor personnel except for a blinded medical monitoring team will be unblinded after the last expected Follow-up Week 4 visit.	See rationale for Section 6.3.3
Throughout	Minor administrative, formatting, grammatical, and typographical changes were made throughout the document.	To ensure clarity and accurate interpretation of the intent of the protocol.

TABLE OF CONTENTS

DOCUMENT HISTORY	3
PROTOCOL AMENDMENT SUMMARY OF CHANGES.....	3
1 PROTOCOL SUMMARY	12
1.1 Synopsis.....	12
1.2 Schema	15
1.3 Schedule of Activities.....	16
1.3.1 Schedule of Activities (Main).....	16
1.3.2 Schedule of Activities (HIV Infection Confirmation or Early Withdrawal From Study)	22
2 INTRODUCTION.....	24
2.1 Study Rationale	24
2.2 Background	24
2.2.1 Pharmaceutical and Therapeutic Background	24

1 PROTOCOL SUMMARY

1.1 Synopsis

Protocol Title: A Phase 2a, Double-Blind, Placebo-Controlled Study to Evaluate the Safety, Tolerability, and Pharmacokinetics of Oral MK-8527 Once Monthly in Participants at Low-Risk for HIV-1 Infection

Short Title: Safety and Pharmacokinetic Study of Oral MK-8527 QM in Participants at Low-Risk for HIV-1 Infection

Acronym: Not applicable

Hypotheses, Objectives, and Endpoints:

There are no hypotheses to be tested in this study.

The following objectives will be evaluated in adults at low-risk of human immunodeficiency virus type 1 (HIV-1) infection.

Primary Objective	Primary Endpoint
To evaluate the safety and tolerability of MK-8527 once monthly (3 mg, 6 mg, and 12 mg) during treatment and through the last follow-up visit.	Adverse events Adverse events leading to discontinuation of study intervention
Secondary Objectives	Secondary Endpoints
To characterize the plasma pharmacokinetic profile of MK-8527 once monthly (3 mg, 6 mg, and 12 mg).	MK-8527 AUC _{0-last} and C _{max}

Overall Design:

Study Phase	Phase 2
Primary Purpose	Treatment
Indication	HIV infection
Population	Adults at low-risk for HIV-1 infection
Study Type	Interventional
Intervention Model	<<Intervention Model>> This is a multi site study.
Type of Control	Placebo

Study Blinding	Double-blind
Blinding Roles	Participants or Subjects Sponsor Investigator
Estimated Duration of Study	The Sponsor estimates that the study will require approximately 58 weeks from the time the first participant (or their legally acceptable representative) provides documented informed consent until the last participant's last study-related contact.

Number of Participants:

Approximately 350 participants will be randomized in a 2:2:2:1 ratio to 1 of 4 intervention groups: Group 1: MK-8527 (3 mg), N=~100; Group 2: MK-8527 (6 mg), N=~100; Group 3: MK-8527 (12 mg), N=~100; Group 4: placebo, N=~50.

Intervention Groups and Duration:

Arm Name	Intervention Name	Unit Dose Strength(s)	Dosage Level(s)	Route of Administration	Regimen/ Treatment Period	Use
Group 1	MK-8527	3 mg	3 mg QM	Oral	Day 1 to Week 20	Test Product
Group 1	Placebo	0 mg	0 mg QM	Oral	Day 1 to Week 20	Placebo
Group 2	MK-8527	3 mg	6 mg QM	Oral	Day 1 to Week 20	Test Product
Group 2	Placebo	0 mg	0 mg QM	Oral	Day 1 to Week 20	Placebo
Group 3	MK-8527	3 mg	12 mg QM	Oral	Day 1 to Week 20	Test Product
Group 4	Placebo	0 mg	0 mg QM	Oral	Day 1 to Week 20	Placebo

QM=once monthly.

Total Number of Intervention Groups/Arms	4 intervention groups (3 active, 1 placebo)
Duration of Participation	Participants will be in the study for approximately 34 weeks from the time the participant provides documented informed consent (for the main study) through the final contact. After a screening phase of up to 45 days (6 weeks), each participant will receive 6 once monthly doses of assigned intervention with the final dose administered at Week 20. All participants will complete an 8-week blinded follow-up period after the last dose.

Study Governance Committees:

Executive Oversight Committee	Yes
Data Monitoring Committee	Yes (Internal)
Clinical Adjudication Committee	No

[figure not shown]
Study governance considerations are outlined in Appendix 1.

Study Accepts Healthy Participants: Yes

A list of abbreviations is in Appendix 10.

1.2 Schema

The study design is depicted in [Figure 1](#).

FU W=follow-up week; N=total number of participants in the study; n=number of participants in each treatment group; PBMC=peripheral blood mononuclear cells; QM=once monthly.

^a A subset of ~20 participants per study intervention group will be included in the PBMC Subset; these participants will have additional in-clinic visits as specified in the SoA (Section 1.3.1).

^b Participants who discontinue study intervention early will be asked to complete the blinded follow-up visits. As per amendment 02, all Sponsor personnel except for a blinded medical monitoring team will be unblinded after the last expected Follow-up Week 4 visit.

^c Randomization to study intervention will occur at Day 1 and will be stratified by sex (female, male) and region (Africa, non-Africa).

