a. Week 1, 2, and 3, and Follow-up Week 6 are in-clinic visits only for participants in the PBMC Subset. At Week 2, participants not in the PBMC Subset will have an AE assessment phone call only (no in-clinic visit is required). b. If Visit 11 is performed as an EOT visit prior to Week 20, all procedures listed should be performed but with the following procedure modifications: 1) no study intervention should be dispensed via the IRT or administered to the participant, 2) only 1 plasma PK sample should be collected at any time during the visit, and if in the PBMC Subset: only 1 PBMC sample and 1 VAMS venous sample should be collected at any time during the visit. c. All participants will attend visits at Follow-up Day 1, Follow-up Week 4 and Follow-up Week 8; the PBMC Subset will also have a visit at Follow-up Week 6. Follow-up visits represent different study weeks for a participant that completes the final Week 20 dose versus a participant that discontinues study intervention prior to Week 20. See Section 8.11.6 for additional details. d. Participants with confirmed decreases in total lymphocyte counts or CD4+ T-cell counts as outlined in Section 7.1, will be followed in the study until they no longer meet the criteria as outlined in Section 8.11.3.1. e. This sample should be drawn for planned analysis of the association between genetic variants in DNA and drug response. This sample will not be collected at that site if there is either a local law or regulation prohibiting collection, or if the IRB/IEC does not approve the collection of the sample for these purposes. If the sample is collected, leftover extracted DNA will be stored for FBR if the participant (or their legally acceptable representative) provides documented informed consent for FBR. If the planned genetic analyses are not approved, but FBR is approved and consent is given, this sample will be collected for the purpose of FBR. f. As per amendment 02, all Sponsor personnel except for a blinded medical monitoring team will be unblinded after the last expected Follow-up Week 4 visit.																	

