4 STUDY DESIGN

4.1 Overall Design

This is a randomized, double-blind, placebo-controlled, parallel-group, multicenter study of oral MK-8527 administered QM in adults who are at low-risk of HIV-1 infection.

Approximately 350 participants will be randomized in a 2:2:2:1 ratio to 1 of 4 intervention groups: Group 1: MK-8527 (3 mg); Group 2: MK-8527 (6 mg); Group 3: MK-8527 (12 mg); and Group 4: Placebo. The screening window is 45 days and participants are allowed to rescreen 1 time (Section 8.11.1.2). The study population composition targets are: $\geq 30\%$ women, $\geq 30\%$ men, $\geq 80\%$ aged ≤ 35 years, and $\geq 30\%$ enrolled in Africa. Randomization will be stratified by sex (female, male) and region (Africa, non-Africa).

Participants will receive a total of 6 oral doses of the assigned blinded study intervention, 1 dose every 4 weeks, starting on Day 1. The final dose will be administered at the Week 20 visit. After the last dose, all participants will complete an 8-week blinded follow-up period.

The primary safety assessment will include all accumulated safety data during the intervention and follow-up period. AEs leading to discontinuation from study intervention will be assessed until Week 20 (last dose received). The Sponsor will perform an ongoing comprehensive review of safety parameters to assess for overall trends and outliers in reported AEs and event toxicities per standard monitoring procedures.

All participants will be evaluated for plasma MK-8527 PK drug levels, and a subset (approximately N=20 participants per intervention group) will be evaluated for MK-8527-TP in PBMC (PBMC Subset).

All participants and the investigators/clinical site personnel directly associated with study conduct will remain blinded to study intervention assignment through the 8-week follow-up period. The siDMC (internal) will be responsible for an interim safety review once 50% of the planned enrollment has reached Week 12 or discontinued from study intervention. Additional meetings of the siDMC may be triggered based on criteria outlined in the SAP/siDMC charter. An unblinded Sponsor team will review PK and safety data on an ongoing basis for the duration of the study. As per amendment 02, all Sponsor personnel except for a blinded medical monitoring team will be unblinded after the last expected Follow-up Week 4 visit, to enable earlier program strategic decision-making by the Sponsor.

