#### **3.5.1.1 Overall Safety Assessment**

The analysis strategy of safety results is summarized in [Table 1](#). The overall safety evaluation will include a summary by intervention group of the number and percentage of participants with at least one AE, SAE, drug-related AE, drug-related SAE, Grade 3 to 4 AE, drug-related Grade 3 to 4 AE, discontinuation from study intervention due to an AE; and AE resulting in death. Point estimates and 95% CIs for the differences between each MK-8527 group and placebo in the percentages of participants with the event will be provided using the M&N method [Miettinen, O. and Nurminen, M. 1985].

For continuous safety measures, such as change from baseline in laboratory values, summary statistics for baseline, on-treatment, and change from baseline values will be provided by treatment group.

The number and percentage of participants with specific AEs will also be provided.

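### The stated PBMC Subset of about 20 per group does not fit 2:2:2:1 randomization; if filled as stated, placebo is observed more closely and crude differences in any AE are pulled slightly downward

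*Protocol*

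**What the plan says.** **Allocation.** Protocol 1.1 states: "Approximately 350 participants will be randomized in a 2:2:2:1 ratio to 1 of 4 intervention groups". The sizes are about 100 for each dose, and for the last two groups "Group 3: MK-8527 (12 mg), N=~100; Group 4: placebo, N=~50". Protocol 6.3.2 stratifies by sex and region only.

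**Subset size.** Protocol 1.2 states: "A subset of ~20 participants per study intervention group will be included in the PBMC Subset; these participants will have additional in-clinic visits". Protocol 4.1 repeats the figure of about 20 per intervention group. Neither section scales it to the allocation ratio. The Schedule of Activities makes participation optional, at preselected sites, with consent at Screening; randomization follows on Day 1.

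**Extra observation.** Footnote a of Protocol 1.3.1 states: "Week 1, 2, and 3, and Follow-up Week 6 are in-clinic visits only for participants in the PBMC Subset". These visits carry AE assessment, hematology, TBNK panel, chemistry and cystatin-C. For everyone else: "At Week 2, participants not in the PBMC Subset will have an AE assessment phone call only (no in-clinic visit is required".

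**Analysis.** SAP 3.5.1.1 plans "Point estimates and 95% CIs for the differences between each MK-8527 group and placebo in the percentages of participants with the event" by the Miettinen-Nurminen (M&N) method, without reference to subset membership. SAP Table 1 lists laboratory changes from baseline and counts of participants passing predefined limits of change (PDLCs) as descriptive only, with no rule on which visits feed the PDLC counts. SAP 3.9 plans no subgroup analyses.

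**The concern.** An equal number per group is an unequal share when the groups differ in size by a factor of two. A participant seen and bled more often has more chances for a mild event to be noted or for a value to cross a limit. Some of those values become AEs, because Protocol 8.3.5 sends clinically relevant laboratory changes to the AE pages.

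If a larger share of placebo is watched closely, the placebo percentage rises with no true difference, and each MK-8527 minus placebo difference shrinks. All three dose comparisons use the same placebo group, so the shift has the same sign in each. In a study whose primary objective is safety, a downward shift is the less cautious direction. The protocol also leaves open whether this imbalance will occur at all, because it does not say how 20 per group is to be reached.

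**Working it through.** **The plan's own figure.** The documents give no figure for the subset shares or for any resulting bias. The nearest is the power of the 100 versus 50 lymphocyte comparison in SAP 3.8.1: 81.8% for a 10% difference with SD 20. A two-sample t-test (noncentral t, 148 df, two-sided 5% assumed) gives 81.8%, so the planned unit of comparison is indeed 100 versus 50.

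**1. Shares if filled as stated.** Placebo 20/50 = 40%; each dose group 20/100 = 20%; active minus placebo = -0.20.

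**2. Extra observation per member.**
- Post-baseline blood counts, all participants: Day 2, Weeks 4, 8, 12, 16 and 20, Follow-up Day 1, Follow-up Weeks 4 and 8 = 9. Members add Weeks 1, 2, 3 and Follow-up Week 6 = 13. Protocol Table 11 agrees: 22 mL of hematology at 2 mL is 11 draws including Screening and Day 1, and the subset adds 8 mL, or 4 draws.
- AE contacts: 9 visits plus the Week 2 call = 10 for non-members; 9 + 4 = 13 for members. So three are added, not four.

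**3. Effect on the percentage with at least one AE.** Let p be the chance of a recorded event on the common schedule, equal in all groups, and d the rise for a member. The active percentage is p + 0.20d and placebo is p + 0.40d, so the difference is -0.20d. The value of d is an assumption.

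| Assumed d (points) | Bias (points) | Coverage of nominal 95% CI | Power, true 30% v 50% |
|---|---|---|---|
| 0 | 0 | 95% | 65% |
| 5 | -1 | about 94.8% | 60% |
| 10 | -2 | about 94.3% | 55% |
| 15 | -3 | not computed | not computed |
| 20 | -4 | about 92% | 45% |

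Coverage is for p of 30% to 70%, by normal approximation. The standard error is 7.3 to 8.7 points. For example, with p = 50% and d = 10: sqrt(0.52 x 0.48/100 + 0.54 x 0.46/50) = 8.6 points.

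**4. Effect on an any-time laboratory count.** With chance q per draw, assumed independent, the chance of at least one flagged value in k draws is 1 - (1 - q)^k, and the bias is -0.20 times the gain from 9 to 13 draws.

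| Assumed q | 9 draws | 13 draws | Bias (points) |
|---|---|---|---|
| 1% | 8.6% | 12.2% | -0.7 |
| 2% | 16.6% | 23.1% | -1.3 |
| 5% | 37.0% | 48.7% | -2.3 |

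Independence puts these towards the high side: if abnormal values cluster in the same people, four more draws add less.

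**5. If the subset simply follows randomization.** With 80 members, each dose group expects 80 x 2/7 = 22.9 and placebo 80/7 = 11.4. That is 80/350 = 23% of every group, so the expected bias is zero. The binomial chance of 20 or more on placebo is about 0.8%. Expecting 20 on placebo needs 20 x 7 = 140 members, with 40 in each dose group, again equal shares.

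**6. Cost of stratifying.** Mantel-Haenszel weights for strata of 20 v 20 and 80 v 30 are 20 x 20/40 = 10.0 and 80 x 30/110 = 21.8, total 31.8. Unstratified, 100 x 50/150 = 33.3. With a common variance, the standard error ratio is sqrt(33.3/31.8) = 1.02.

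**The case against.** The strongest reply is that the 40%/20% split is not established. Consent at Screening followed by blinded 2:2:2:1 randomization makes membership independent of group, so shares should be about equal (step 5). A split of 40/20 needs enrolment into the subset to depend on the assigned group, and neither document describes that. This stands. It makes the bias conditional, and leaves the stated placebo number as the thing that fails instead.

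A second reply is that many outputs are untouched. This also stands. A reader might infer that the AE and laboratory comparisons as a whole are biased towards hiding harm. The documents do not support that:
- Mean change at a visit everyone attends does not depend on extra visits elsewhere.
- The 10% criterion in SAP 3.6 is computed within a group, not against placebo.
- SAP Table 1 plans no between-group interval for laboratory values. Only any-time or worst-value summaries are exposed: PDLC counts, or the interim lymphocyte interval if it were based on a nadir. The SAP defines neither.
- Deaths, SAEs and Grade 3 to 4 events would mostly be captured at the common visits. The extra visits include no physical examination or vital signs, and all AEs from randomization onward must be reported whenever they are learned of.

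A third reply is that the size is assumed and small beside the standard error. That is right, and it limits the weight of the point. It does not remove the point: the shift would be systematic and is cheap to prevent.

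**Conclusion.** The concern holds conditionally. The stated subset size and the stated allocation cannot both be met by the procedure described, so one of two things follows:
- **Filled as stated:** observation is unequal, and the crude differences in the percentage with any AE, and any any-time laboratory count, are shifted by -0.20 times the extra detection. Assumed gains of 5 to 15 points give -1 to -3 points for any AE; assumed per-draw chances of 1% to 5% give -0.7 to -2.3 points for a laboratory count. The shift is zero if the extra visits detect nothing more.
- **Filled by randomization:** no bias is expected, but a subset of 80 has about 11 on placebo, not 20.

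The shares and visit counts come from the documents; the detection gains do not. The effect is modest, bears mainly on any AE, and should be little for the serious and severe categories. It is worth correcting because it falls on the primary endpoint and would shrink an excess on MK-8527.

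**What to change.** 1. **Protocol 1.2 and 4.1:** reconcile the figure of about 20 per group with the 2:2:2:1 allocation. Either state how the subset is filled, or restate the expected number in each group.
2. **SAP 3.5.1.1:** compute the M&N differences stratified by PBMC Subset membership as recorded at Day 1, with Mantel-Haenszel weights. Day 1 status is preferable to later status because subset consent can be withdrawn (Protocol 8.1.1.3), after which the participant reverts to the standard visits. It is also preferable to consent alone, which would not fix membership if numbers were capped by group.
3. **SAP Table 1:** base between-group PDLC and other any-time laboratory counts on visits common to all participants. Show the subset-only visits separately, so that no safety data are dropped.

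The cost is SAP wording, a little programming, a clarification in the protocol, and intervals about 2% wider if the strata are 20 v 20 and 80 v 30.

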1.3 Schedule of Activities

1.3.1 Schedule of Activities (Main)

Study Period	Screening	Study Intervention (Blinded)											Follow-up (Blinded) ^f				Notes
		1	2	3	4	5	6	7	8	9	10	11	12	13	14	15	
Visit Number	Screening	Day 1	Day 2	Week 1 ^a	Week 2 ^a	Week 3 ^a	Week 4	Week 8	Week 12	Week 16	Week 20/ EOT ^b	Follow-up Day 1 ^c	Follow-up Week 4 ^c (Week 24)	Follow-up Week 6 ^c (Week 26)	Follow-up Week 8 ^c (Week 28)		
Scheduled Day/Week																	
Window	≤45 days	N/A	N/A	±2 days			±7 days			N/A	±7 days	±2 days	±7 days				
Administrative Procedures																	
Informed consent	X																Informed consent marks the start of the screening window.
Informed consent for FBR	X																
Inclusion/exclusion criteria	X	X															Participants may be rescreened 1 time; see Section 8.11.1.2.
Participant identification card	X	X															Add randomization number on Day 1.
Register study visit in IRT	X	X					X	X	X	X	X						
Randomization		X															
Dispense study intervention using IRT and administer study intervention		X					X	X	X	X	X						Directly observed dosing. Add randomization number and visit number to the bottles at time of dispensing.
Offer condoms and lubricant		X					X	X	X	X	X		X				For sexually active participants. Document in participant chart.
Safety Procedures																	
Medical history	X	X															

Study Period	Screening	Study Intervention (Blinded)											Follow-up (Blinded) ^f				Notes
		1	2	3	4	5	6	7	8	9	10	11	12	13	14	15	
Visit Number																	
Scheduled Day/Week	Screening	Day 1	Day 2	Week 1 ^a	Week 2 ^a	Week 3 ^a	Week 4	Week 8	Week 12	Week 16	Week 20/ EOT ^b	Follow-up Day 1 ^c	Follow-up Week 4 ^c (Week 24)	Follow-up Week 6 ^c (Week 26)	Follow-up Week 8 ^c (Week 28)		
Window	≤45 days	N/A	N/A	±2 days			±7 days			N/A	±7 days	±2 days	±7 days				
HIV infection risk evaluation	X	X					X	X	X	X	X		X		X	Document in participant chart. Assess as per Inclusion Criterion #2 at Screening and Day 1 (prior to dose). After Day 1, assess changes in risk status and PrEP eligibility using Appendix 8.	
Prior/concomitant medication review	X	X	X	X	X	X	X	X	X	X	X	X	X	X	X		
Contraceptive use confirmation (POCBP only)	X	X					X	X	X	X	X		X		X	Document in participant chart.	
Complete physical exam	X																
Symptom-directed physical exam		X	X				X	X	X	X	X		X		X		
Vital signs	X	X	X				X	X	X	X	X		X		X	Includes body temperature, pulse, respiratory rate, and systolic and diastolic blood pressure.	
Height	X																
Weight	X	X					X	X	X	X	X		X		X		
AE assessment	X	X	X	X	X	X	X	X	X	X	X	X	X	X	X	Assess before and after dose on Day 1.	
AE assessment phone call (participants not in PBMC Subset)					X											Participants not in the PBMC Subset will have this AE assessment phone call (no in-clinic visit is required).	

Study Period	Screening	Study Intervention (Blinded)											Follow-up (Blinded) ^f				Notes
		1	2	3	4	5	6	7	8	9	10	11	12	13	14	15	
Visit Number																	
Scheduled Day/Week	Screening	Day 1	Day 2	Week 1 ^a	Week 2 ^a	Week 3 ^a	Week 4	Week 8	Week 12	Week 16	Week 20/ EOT ^b	Follow-up Day 1 ^c	Follow-up Week 4 ^c (Week 24)	Follow-up Week 6 ^{a,c} (Week 26)	Follow-up Week 8 ^c (Week 28)		
Window	≤45 days	N/A	N/A	±2 days			±7 days			N/A	±7 days	±2 days	±7 days				
12-lead ECG	X										X					Perform postdose at Week 20. Perform at EOT if participant discontinues study intervention early.	
Laboratory Evaluations/Procedures																	
HIV-1 and HIV-2 screen	X	X					X	X	X	X	X		X		X	Participants with a positive HIV-1/2 screen test will require additional testing. See Section 8.3.4.1.	
HBV and HCV testing	X																
Syphilis serologic testing	X																
Urine GC/CT & trichomoniasis testing (females only)	X																
Urine GC/CT testing (males only)	X																
PT/INR	X																
Serum pregnancy test (β-hCG) (POCBP only)	X															Performed by central laboratory per local regulations. If results are inconclusive, additional testing and/or verification of medical history will be required to confirm eligibility.	

Study Period	Screening	Study Intervention (Blinded)											Follow-up (Blinded) ^f				Notes
		1	2	3	4	5	6	7	8	9	10	11	12	13	14	15	
Visit Number	Screening	Day 1	Day 2	Week 1 ^a	Week 2 ^a	Week 3 ^a	Week 4	Week 8	Week 12	Week 16	Week 20/ EOT ^b	Follow-up Day 1 ^c	Follow-up Week 4 ^c (Week 24)	Follow-up Week 6 ^{a,c} (Week 26)	Follow-up Week 8 ^c (Week 28)		
Scheduled Day/Week	Screening																
Window	≤45 days	N/A	N/A	±2 days			±7 days			N/A	±7 days	±2 days	±7 days				
Urine pregnancy test (POCBP only)		X					X	X	X	X	X		X		X	Mandatory and performed locally as per local regulations and prior to administering/dispensing study intervention. Do NOT dispense study intervention if urine pregnancy test is positive. Confirm with serum test if urine test is positive.	
Hematology ^d	X	X	X	X	X	X	X	X	X	X	X	X	X	X	X		
TBNK Panel/CD4+ T-cell count ^d	X	X	X	X	X	X	X	X	X	X	X	X	X	X	X		
Chemistry	X	X		X	X	X	X	X	X	X		X	X	X			
Creatinine clearance calculation (CG)	X	X		X	X	X	X	X	X	X		X	X	X			
Cystatin-C	X	X		X	X	X	X	X	X	X	X		X	X	X		
Pharmacokinetics (All Participants)																	
Plasma PK sample collection(s)		X	X									X	X			Some visits require more than 1 sample collection. See Section 8.6 for additional details.	
Pharmacokinetics (Participants NOT in the PBMC Subset)																	
Venous microsampling (eg, Mitra [®] /VAMS)							X	X	X	X	X					See Section 8.6 for additional details.	

Study Period	Screening	Study Intervention (Blinded)											Follow-up (Blinded) ^f				Notes
		1	2	3	4	5	6	7	8	9	10	11	12	13	14	15	
Visit Number																	
Scheduled Day/Week	Screening	Day 1	Day 2	Week 1 ^a	Week 2 ^a	Week 3 ^a	Week 4	Week 8	Week 12	Week 16	Week 20/ EOT ^b	Follow-up Day 1 ^c	Follow-up Week 4 ^c (Week 24)	Follow-up Week 6 ^{a,c} (Week 26)	Follow-up Week 8 ^c (Week 28)		
Window	≤45 days	N/A	N/A	±2 days			±7 days			N/A	±7 days	±2 days	±7 days				
Pharmacokinetics (PBMC Subset)																Participation in the PBMC Subset will be optional. Participants are from preselected sites. Refer to operation/laboratory manual for sample handling requirements.	
Informed consent for PBMC Subset sample collection	X																
PBMC collection		X	X	X	X	X	X	X	X	X	X	X	X	X	X	Some visits require more than 1 sample collection. See Section 8.6 for additional details.	
Venous microsampling (eg, Mitra [®] /VAMS)		X	X	X	X	X	X	X	X	X	X	X	X	X	X	See Section 8.6 for additional details	

Study Period	Screening	Study Intervention (Blinded)											Follow-up (Blinded) ^f				Notes
		1	2	3	4	5	6	7	8	9	10	11	12	13	14	15	
Visit Number	Scheduled Day/Week	Screening	Day 1	Day 2	Week 1 ^a	Week 2 ^a	Week 3 ^a	Week 4	Week 8	Week 12	Week 16	Week 20/ EOT ^b	Follow-up Day 1 ^c	Follow-up Week 4 ^c (Week 24)	Follow-up Week 6 ^{a,c} (Week 26)	Follow-up Week 8 ^c (Week 28)	
Window	≤45 days	N/A	N/A		±2 days					±7 days		N/A	±7 days	±2 days	±7 days		
Biomarkers																	
Blood for genetic analysis ^e		X															Collect predose from enrolled participants only
AE=adverse event; β-hCG=beta human chorionic gonadotropin; CG=Cockcroft-Gault; CT=chlamydia trachomatis; DNA=deoxyribonucleic acid; ECG=electrocardiogram; EOT=End of Treatment; FBR=future biomedical research; GC=Neisseria gonorrhoeae; HBV=hepatitis B virus; HCV=hepatitis C virus; HIV=human immunodeficiency virus; IEC=Independent Ethics Committee; INR=International Normalized Ratio; IRB=Institutional Review Board; IRT=Interactive Response Technology; N/A=not applicable; PBMC=peripheral blood mononuclear cells; PK=pharmacokinetic; POCBP=participants of childbearing potential; PrEP=pre-exposure prophylaxis; PT=prothrombin time; TBNK=T- and B-lymphocyte natural killer cell; VAMS=volumetric absorptive microsampling.																	
a. Week 1, 2, and 3, and Follow-up Week 6 are in-clinic visits only for participants in the PBMC Subset. At Week 2, participants not in the PBMC Subset will have an AE assessment phone call only (no in-clinic visit is required). b. If Visit 11 is performed as an EOT visit prior to Week 20, all procedures listed should be performed but with the following procedure modifications: 1) no study intervention should be dispensed via the IRT or administered to the participant, 2) only 1 plasma PK sample should be collected at any time during the visit, and if in the PBMC Subset: only 1 PBMC sample and 1 VAMS venous sample should be collected at any time during the visit. c. All participants will attend visits at Follow-up Day 1, Follow-up Week 4 and Follow-up Week 8; the PBMC Subset will also have a visit at Follow-up Week 6. Follow-up visits represent different study weeks for a participant that completes the final Week 20 dose versus a participant that discontinues study intervention prior to Week 20. See Section 8.11.6 for additional details. d. Participants with confirmed decreases in total lymphocyte counts or CD4+ T-cell counts as outlined in Section 7.1, will be followed in the study until they no longer meet the criteria as outlined in Section 8.11.3.1. e. This sample should be drawn for planned analysis of the association between genetic variants in DNA and drug response. This sample will not be collected at that site if there is either a local law or regulation prohibiting collection, or if the IRB/IEC does not approve the collection of the sample for these purposes. If the sample is collected, leftover extracted DNA will be stored for FBR if the participant (or their legally acceptable representative) provides documented informed consent for FBR. If the planned genetic analyses are not approved, but FBR is approved and consent is given, this sample will be collected for the purpose of FBR. f. As per amendment 02, all Sponsor personnel except for a blinded medical monitoring team will be unblinded after the last expected Follow-up Week 4 visit.																	

